**Table 2: Dose Modification Instructions for Pomalidomide**

Toxicity a	Dose Modification
Neutropenia Grade 4 neutropenia (ANC < 500/ $\mu$ L) or Febrile neutropenia (ANC < 1,000/ $\mu$ L with a single temperature of > 38.5 °C or a sustained temperature of $\geq$ 38 °C for more than one hour)	Withhold the dose and follow CBC weekly. If the subject was not receiving GCSF therapy, GCSF therapy may be started at the discretion of the treating physician. When dosing is resumed, the dose of POM may be maintained if neutropenia was the only POM-related toxicity requiring a dose modification and GCSF treatments are continued. Otherwise, decrease by one dose level. Note, ANC must be $\geq$ 500/ $\mu$ L to restart dosing For Cohort C, ANC must be $\geq$ 1000/ $\mu$ L to restart dosing
Thrombocytopenia Grade 4 thrombocytopenia (Platelets < 25,000/ $\mu$ L)	Withhold the dose and follow CBC weekly. Dosing may resume at one dose level lower once the platelet count has recovered to $\geq$ 50,000/ $\mu$ L.

**Table 2: Dose Modification Instructions for Pomalidomide (Continued)**

Toxicity	Dose Modification
Rash, Grade 3	Withhold dose for remainder of cycle. Decrease by one dose level when dosing restarted at next cycle (rash must resolve to $\leq$ Grade 1 before restarting dosing).
Rash, Grade 4 or Blistering	Discontinue subject from study treatment.
VTE $\geq$ Grade 3	Withhold dose for remainder of cycle. Assess anticoagulation treatment. Maintain dose level when dosing restarted at next cycle at discretion of treating physician.
Other $\geq$ Grade 3 POM-related b adverse events	Withhold dose. Decrease by one dose level when dosing restarted (adverse event must resolve to $\leq$ Grade 2 before restarting dosing).

ANC = absolute neutrophil count; GCSF = granulocyte colony-stimulating factor; POM = pomalidomide; VTE = venous thromboembolism.

a If recovery from toxicities is prolonged beyond 14 days, then the dose of POM will be decreased by one dose level when dosing is restarted.

b For Grade 3 or 4 AEs that are not considered to be related to study drug, the treating physician should consult with the sponsor for dose interruptions and reductions.

To initiate a new cycle of POM, the neutrophil count must be  $\geq 500/\mu\text{L}$  and for Cohort C, the neutrophil count must be  $\geq 1000/\mu\text{L}$  with or without granulocyte colony-stimulating factor (GCSF), the platelet count must be  $\geq 50,000/\mu\text{L}$ , and non-hematologic AEs must have recovered as outlined in [Table 2](#).

If recovery from toxicities is prolonged beyond 14 days, then the dose of POM will be decreased by one dose level when dosing is restarted. Prior to restarting treatment after a prolonged delay, subjects should be assessed to ensure they have not developed progressive disease.

**Table 3: Pomalidomide Dose Reduction Steps**

Dose Level a	Oral POM Dose Reduction (Days 1-21 of 28 days)
Starting dose	4 mg
Dose Level -1	3 mg
Dose Level -2	2 mg
Dose Level -3	1 mg

a The minimum permitted dose level for POM is 1.0 mg. No dose re-escalation is permitted for Pomalidomide.

### Dose Modification Instructions for Low-dose Dexamethasone

Dose Reductions for Low-dose dexamethasone-related Toxicities ([Table 4](#)) details instructions for LD-dex dose interruptions and reductions and [Table 5](#) outlines the dose reduction steps for LD-dex; however, the full product information and labeling contained in the current dex Package Insert should also be reviewed.

If LD-dex is held or permanently discontinued due to toxicity, POM, and (for patients in Cohort B and Cohort C) DARA may be continued.

**Table 4: Dose Reductions for Low-dose Dexamethasone-related Toxicities**

Toxicity a	LD-dex Dose Modification
Dyspepsia = Grade 1-2	Maintain dose and treat with histamine (H2) blockers or equivalent. Decrease by one dose level if symptoms persist.
Dyspepsia ≥ Grade 3	Withhold dose until symptoms are controlled. Add H2 blocker or equivalent and decrease one dose level when dose restarted.
Edema ≥ Grade 3	Use diuretics as needed and decrease dose by one dose level.
Confusion or mood alteration ≥ Grade 2	Withhold dose until symptoms resolve. When dose restarted, decrease dose by one dose level.
Muscle weakness (steroid myopathy) ≥ Grade 2	Withhold dose until muscle weakness ≤ Grade 1. When dose restarted decrease dose by one dose level.
Hyperglycemia ≥ Grade 3	Decrease dose by one dose level. Treat with insulin or oral hypoglycemic agents as needed.
Acute pancreatitis	Discontinue subject from dex treatment regimen.
Other ≥ Grade 3 dex-related adverse events	Stop dex dosing until the adverse event resolves to ≤ Grade 2. Decrease by one dose level when dex dosing is resumed.

a If recovery from toxicities is prolonged beyond 14 days, then the dose of dex will be decreased by one dose level when dose is restarted.

**Table 5: Dexamethasone Dose Reduction Steps**

Dose Level a	≤ 75 Years Old Dose (Days 1, 8, 15, 22 of a 28-day Cycle)	> 75 Years Old Dose (Days 1, 8, 15, 22 of a 28-day Cycle)
Starting Dose	40 mg	20 mg
Dose Level -1	20 mg	12 mg
Dose Level -2	10 mg	8 mg

a Dexamethasone should be discontinued if subject is unable to tolerate 10 mg if ≤ 75 years old or 8 mg if > 75 years old.

### 8.3. Daratumumab Administration

Preparation of the infusion bags should be done on the day of the planned infusion. The infusion solution will be prepared as a 1000-mL (first dose only) or 500-mL dilution of daratumumab in sterile, pyrogen free 0.9% NaCl. Preparation of the infusion bags should be done on the day of the planned infusion. Daratumumab must be administered as an IV infusion given through a well-functioning IV catheter by using an infusion pump or syringe pump. The study drug must be filtered by using an inline filter (0.2 µM) during the infusion.

Each subject's dose will be calculated based on the subject's weight rounded to the nearest kilogram. Dosing calculations do not need to be changed for weight changes that are < 10% from baseline. For reconstitution, administration and storage after reconstitution information, please refer to the pharmacy manual.

## Recommended Concomitant Medications

### Pre-infusion Medication

Administer pre-infusion medications to reduce the risk of infusion reactions to all subjects approximately 1 hour prior to every infusion of DARA as follows:

- Protocol specified dose of oral dexamethasone, plus
- oral antipyretics (acetaminophen 650 to 1000 mg), plus
- oral or intravenous antihistamine (diphenhydramine 25 to 50 mg or equivalent).
- Oral leukotriene receptor antagonist (10 mg montelukast or equivalent) is also recommended as this may reduce infusion related reactions ([Van de Donk, 2016](#)).

### Post-infusion Medication

For subjects with a history of obstructive pulmonary disorder, consider prescribing post-infusion medications such as short and long-acting bronchodilators, and inhaled corticosteroids.

Following the first four infusions, if the patient experiences no major infusion reactions, these additional inhaled post-infusion medications may be discontinued.

Where clinically indicated, at the discretion of the investigator, initiate antiviral prophylaxis to prevent herpes zoster reactivation within 1 week of starting DARA and continue for 3 months following treatment

### Daratumumab Dose Modifications

For infusion reactions of any grade/severity, immediately interrupt the DARA infusion and manage symptoms. Management of infusion reactions may further require reduction in the rate of infusion, or treatment discontinuation of DARA as outlined below ([Table 6](#)).

- Grade 1-2 (mild to moderate): Once reaction symptoms resolve, resume the infusion at no more than half the rate at which the reaction occurred. If the patient does not experience any further reaction symptoms, infusion rate escalation may resume at increments and intervals as appropriate ([Table 6](#)).
- Grade 3 (severe): If the intensity of the reaction decreases to Grade 2 or lower, consider restarting the infusion at no more than half the rate at which the reaction occurred. If the patient does not experience additional symptoms, resume infusion rate escalation at increments and intervals as outlined in [Table 6](#). Repeat the procedure above in the event of recurrence of Grade 3 symptoms. Permanently discontinue DARA upon the third occurrence of a Grade 3 or greater infusion reaction.
- Grade 4 (life threatening): Permanently discontinue DARA treatment.

During a cycle, a daratumumab dose must be held if any of the following criteria below are met, to allow for recovery from toxicity. The criteria for a dose delay are:

- Grade 4 hematologic toxicity, or Grade 3 or higher thrombocytopenia with bleeding;
- Febrile neutropenia of any grade;
- Neutropenia with infection, of any grade;

- Grade 3 or higher nonhematologic toxicities with the following exceptions:
  - Grade 3 nausea or Grade 3 vomiting that responds to antiemetic treatment,
  - Grade 3 diarrhea that responds to antidiarrheal treatment,
  - Isolated Grade 3 Gamma-glutamyltransferase elevation
  - Grade 3 fatigue or asthenia that was present at baseline or that lasts for < 7 days after the last administration of daratumumab

If daratumumab administration does not commence within the prespecified window (Table 6) of the scheduled administration date, then the dose will be considered a missed dose.

Administration may resume at the next planned dosing date.

**Table 6: Daratumumab-Related Toxicity Management**

Frequency	Dose Miss	Dosing Resumption
Weekly	> 3 days	next planned weekly dosing date
Every 3 weeks	> 14 days	next planned every-third-week dosing date
Every 4 weeks	> 21 days	next planned every-4-weeks dosing date

A missed dose will not be made up. Any dose holds of more than 14 days due to toxicity will result in permanent discontinuation of daratumumab. Dose holds of more than 14 days for other reasons should be discussed with the sponsor. If a dose delay occurs, pharmacodynamic assessments should be performed on the actual day of study drug administration (only on days that PD samples are scheduled per protocol), not on the original scheduled administration day.

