**Table 1: Table of Events (Continued)**

Procedures	Screening (Days -28 to 0)	Day 1 (± 3 days) of Every 28-day Cycle	Cycle 1 & 2 Day 8 (± 3 days) Day 15 (± 3 days) Day 22 (± 3 days)	Cycle 3, 4, 5, 6 Day 15 (± 3 days)	Treatment Discontinuation on Visit (± 3 days)	Follow-up Visit (Within 28 Days Post Treatment Discontinuation) (± 3 days)	Long-term Follow-up Every 3 Months (84 ± 14 days) for Up to 5 Years After Last Subject Enrollment in each respective cohort
Other Assessments							
Exploratory biomarker sampling: whole blood (at selected sites) t	X	X t	X t	-	X t	-	-
Exploratory biomarker sampling: bone marrow aspirate (at selected sites) t	X	-	-	-	X	-	-
Exploratory biomarker sampling: normal tissue (saliva samples) at selected sites u	X	-	-	-	-	-	-
EQ-5D (for subjects enrolling in Cohort B) v	X	X v	-	-	X	-	-
Investigational Product Dispensation							
Oral POM dispensation/ accountability	-	X	-	-	X	-	-
Oral dex dispensation/ accountability	-	X	-	-	X	-	-
DARA intravenous dispensation/infusion/ accountability	-	X	X	X	X	-	-

ANC = absolute neutrophil count; ALC = absolute lymphocyte count; ALT = alanine aminotransferase; AST = aspartate aminotransferase; BUN = blood urea nitrogen; CR = complete response; CT = computed tomography; dex = dexamethasone; ECG = electrocardiogram; ECOG = Eastern Cooperative Oncology Group; eCRF = electronic case report forms; FCBP = females of childbearing potential; GGT = gamma glutamyl transferase; HGB = Hemoglobin; HCT = Hematocrit; IAT = indirect antiglobulin test; ICD = Informed Consent Document; LD = low-dose; LDH = lactate dehydrogenase; MCV = mean corpuscular volume; MM = multiple myeloma; MRI = magnetic resonance imaging; PD = progressive disease; POM = Pomalidomide; PR = partial response; RBC = red blood cell; SAE = serious adverse event; SGOT = serum glutamic oxaloacetic transaminase; SGPT = serum glutamic pyruvic transaminase; SPM = second primary malignancy; VTE = venous thromboembolism; WBC = white blood cell.

a Results for any local cytogenetic testing, if available as part of medical history, will be collected in the electronic case report forms (eCRFs).

b Date of initial diagnosis and myeloma stage per the International Staging System and/or the Durie-Salmon Staging System ([Appendix H](#)) at initial diagnosis (if available) will be collected as part of the disease diagnosis assessment.

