### **8.2. Treatment Administration and Schedule**

All study drug doses will be administered orally or intravenously, and subjects will be instructed about the dosing schedules for the study.

Subjects enrolled in Cohort A of this study will receive:

- Oral POM at the starting dose of 4 mg/day on Days 1-21 of a 28-day cycle
- Oral LD-dex at the starting dose of 40 mg/day ( $\leq$  75 years old) or 20 mg/day ( $>$  75 years old) on Days 1, 8, 15, and 22 of a 28-day cycle.

Subjects enrolled in Cohort B and Cohort C of this study will receive:

- Oral POM at the starting dose of 4 mg/day on Days 1-21 of a 28-day cycle
- Oral LD-dex at the starting dose of 40 mg/day ( $\leq$  75 years old) or 20 mg/day ( $>$  75 years old) on Days 1, 8, 15, and 22 of a 28-day cycle.
- DARA administered intravenously at a starting dose of 16 mg/kg at following schedule:
  - Days 1, 8, 15, and 22 of a 28-day cycle for Cycle 1 and Cycle 2
  - Days 1 and 15 for Cycle 3 through Cycle 6
  - Day 1 for Cycle 7 and each cycle thereafter until disease progression

Subjects will also be instructed to return the study drug bottles (and any remaining study drug) at the next visit for drug accountability purposes. For FCBP, study drug will not be dispensed until the investigator has verified that the results of the pregnancy test are negative. Females of childbearing potential other than the subject should not handle study drug unless wearing gloves.

All subjects enrolled into the study will continue study treatment until progressive disease or unacceptable toxicity, death, withdrawal of active participation in the study or withdrawal of consent, or lost to follow-up, or as long as they benefit from therapy according to the opinion of the responsible study investigator.

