### Dose Modification and Interruption

Dosing interruptions and reductions are permitted throughout the study.

In the event of any dose reduction for POM, site staff must contact the Interactive Voice Response System (IVRS) to record the new dose level.

If the treatment has been interrupted and the next cycle is delayed beyond 28 days after Day 1 of the prior cycle, then Day 1 of the next cycle will be defined as the first day that treatment is resumed.

Subjects will be evaluated for AEs at each visit with the NCI-CTCAE (version 4.03) as a guide for the grading of severity.

- If POM is permanently discontinued, then the subject must be permanently discontinued from all study treatments.
- For Patients in Cohort B and Cohort C, if DARA is withheld or permanently discontinued, then POM, and LD-Dex dosing may be continued.
- If LD-dex dosing is withheld or permanently discontinued, then POM and DARA (for patients in Cohort B and Cohort C) dosing may be continued.

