### **Daratumumab Interruption or Missed Doses**

A daratumumab dose that is held for more than 3 days per the per-protocol administration date for any reason other than toxicities suspected to be related to daratumumab should be brought to the attention of the sponsor's Study Manager at the earliest possible time. Subjects missing  $\geq 3$  consecutive planned doses of daratumumab should be withdrawn from study treatment, unless, upon consultation with the sponsor and the review of safety and efficacy, continuation is agreed upon.

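### Table 6 sets no missed-dose threshold for every-2-week daratumumab (Cycles 3–6) and has an every-3-week row that fits no scheduled dose

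*Combined protocol and SAP*

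**What the plan says.** Section 8.2 schedules daratumumab for Cohorts B and C weekly in Cycles 1 and 2, then "Days 1 and 15 for Cycle 3 through Cycle 6", then on Day 1 of each cycle from Cycle 7. The Protocol Summary and Section 4.1 agree.

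Section 8.3 makes Table 6 the test for a missed dose: "If daratumumab administration does not commence within the prespecified window (Table 6) of the scheduled administration date", the dose counts as missed and dosing may resume at the next planned date. Table 6 has three rows:

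- weekly: missed after more than 3 days;
- every 3 weeks: missed after more than 14 days, with resumption at the "next planned every-third-week dosing date";
- every 4 weeks: missed after more than 21 days.

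The text below the table adds "A missed dose will not be made up". It also ends daratumumab permanently after a toxicity hold of more than 14 days, and sends other holds of that length to the sponsor for discussion.

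Four other provisions touch the every-2-week phase:

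- Table 1 lists its Day 15 infusions under a column that begins "Cycle 3, 4, 5, 6 Day 15 (± 3 days"; Day 1 of every cycle also has ±3 days.
- Section 8.2 says that when treatment is interrupted and the next cycle is delayed, "Day 1 of the next cycle will be defined as the first day that treatment is resumed".
- Section 8.2 also says "if DARA is withheld or permanently discontinued, then POM, and LD-Dex dosing may be continued".
- Section 8.3 asks sites to tell the sponsor of any hold over 3 days "for any reason other than toxicities suspected to be related to daratumumab". Three or more consecutive missed doses lead to withdrawal from treatment unless the sponsor agrees to continue.

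**The concern.** Sites are sent to Table 6 to learn whether a late infusion is still given or is skipped, and for one of the three dosing phases the table has no answer. The row in that position describes an interval this study never uses. A site holding a Day 15 dose in Cycle 4 must either fall back on the Table 1 visit window or borrow the nearest row. Those two choices give very different limits (3 days and 14 days).

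Two things are at stake: consistent dosing between sites, and the spacing between consecutive infusions. The gap matters most for holds prompted by suspected daratumumab toxicity, because the 3-day notice to the sponsor does not cover them.

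**Working it through.** The plan gives no figure for this phase, so there is nothing to reproduce. The check sets the schedule in Section 8.2 against Table 6.

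**1. Planned infusions and intervals**

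- Cycles 1–2: 2 × 4 = 8 infusions, 7 days apart.
- Cycles 3–6: 4 × 2 = 8 infusions. Day 1 to Day 15 is 15 − 1 = 14 days. Day 15 to the next Day 1 is 29 − 15 = 14 days, including Cycle 6 Day 15 to Cycle 7 Day 1.
- Cycle 7 onward: one infusion every 28 days.
- Total through Cycle 6: 8 + 8 = 16. A 21-day interval never occurs.

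**2. Schedule against Table 6**

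| Interval | Scheduled? | Table 6 window | Days left to next dose |
|---|---|---|---|
| 7 days | Cycles 1–2 | 3 days | 7 − 3 = 4 |
| 14 days | Cycles 3–6 | none | undefined |
| 21 days | never | 14 days | 21 − 14 = 7 |
| 28 days | Cycle 7 on | 21 days | 28 − 21 = 7 |

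**3. Infusions affected**

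- Day 15 doses of Cycles 3–6: 4 of 16 = 25%. Their planned date does not move with a cycle restart.
- Day 1 doses of Cycles 3–6: 4 more, but only when daratumumab alone is held. If the whole treatment is interrupted and the cycle is delayed, Day 1 moves with it and the question does not arise. Upper bound: 4 + 4 = 8 of 16 = 50%.
- The denominator stops at Cycle 6. Later infusions fall under the every-4-week row, so the share of all infusions is smaller for subjects who continue.

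**4. Delays left unclassified**

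Up to day 3 the dose is inside the Table 1 window. On day 14 the next dose is due. Between them lie days 4 to 13, which is 13 − 4 + 1 = 10 days.

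**5. Can the visit window stand in?**

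Not reliably. Day 1 of Cycle 7 and later carries the same ±3 days in Table 1, yet Table 6 calls that dose missed only after 21 days. The plan therefore does not treat the visit window as the missed-dose threshold for every-4-week dosing, and nothing says that it does for every-2-week dosing.

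**6. Can the spare row be borrowed?**

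No. A 14-day window in a 14-day interval leaves 14 − 14 = 0 days. A dose given 13 days late would nominally fall 14 − 13 = 1 day before the next. The rows in Table 6 leave at least 4 or 7 days. For comparison, a 7-day threshold leaves 14 − 7 = 7 days and a 10-day threshold leaves 14 − 10 = 4.

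**7. The every-4-week row against the text below it**

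For a toxicity hold of 15 to 21 days, the row treats the dose as still giveable, while the sentence below the table has already stopped the drug permanently. The overlap is 21 − 14 = 7 days.

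**The case against.** The strongest reply is that the text has a conservative default. Table 1 gives ±3 days for these infusions and Section 8.3 says that dosing may resume at the next planned date, so a dose more than 3 days late is outside the only written window and should be skipped. The Cycle 7 comparison shows that an explicit row can extend the visit window. It does not prove that the window lapses where there is no row. This stands in part: a careful site has a cautious course open to it, and it would go too far to say that the plan gives no guidance. But Section 8.3 names Table 6, not Table 1, as the source of the window, so the default is an inference.

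The consequences are also bounded. Non-toxicity holds over 3 days reach the sponsor, and toxicity holds over 14 days end daratumumab. A single hold of 4–13 days concerns one infusion, so by itself it cannot reach the rule on three consecutive missed doses. All of that stands.

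A reader might infer that half of the early infusions lack a rule. The documents support that only as an upper bound. Some daratumumab hold triggers in Section 8.3 (febrile neutropenia, Grade 4 neutropenia and thrombocytopenia) also hold pomalidomide under Table 2, and when the cycle is then delayed Day 1 moves with it.

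**Conclusion.** The point holds as a minor correction to a dosing rule. Table 6 has one row that applies to no dose, and it lacks a row for a scheduled phase. The missed-dose threshold is undefined for 4 of the first 16 infusions, rising to at most 8 of 16 when daratumumab alone is held, for delays of 4–13 days. The row is complete and states its interval twice, so a reading error in the text is unlikely.

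Three stronger readings are not supported:

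- **An effect on the overall response rate, or a number of affected subjects.** The documents do not say how often such holds occur, and the sample sizes and tests in Section 10 do not depend on this rule.
- **A 7-day threshold implied by the plan.** No section gives one. By the spacing that the weekly row leaves, 10 days could be argued equally well.
- **The rest of Table 6 as sound.** The every-4-week window conflicts with the 14-day toxicity rule directly below it.

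The practical benefit lies mainly with Cohort C (about 20 subjects), since enrollment to Cohort B is complete at 112. The conclusion assumes only that the schedule in Section 8.2, repeated consistently elsewhere, is the intended one.

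**What to change.** Replace the every-3-week row of Table 6 with: Every 2 weeks | > X days | next planned every-2-week dosing date. The sponsor's medical team should set X below 14. A value of 7 would keep 7 days to the next dose, the same margin that the every-4-week row leaves.

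In the same edit, state that the window of more than 21 days for every-4-week dosing applies only to non-toxicity holds, because toxicity holds of more than 14 days already require permanent discontinuation.

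The cost is one table row and one clarifying note in the next amendment. No visit, procedure or subject is added.
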